### **TRACE RA-DAS secondary endpoints**

DMARD (Disease Modifying and Anti-Rheumatic Drugs) changes DAS 28 at month 12 and 24. Functional outcome assessed by HAQ and EQ5D at month 6, 12 and 24.

### 3.3 Trial intervention

Active treatment: Atorvastatin 40mg once daily with **Placebo** consisting of dummy atorvastatin once daily (both provided by Pfizer UK Ltd). All patients are counselled about modifiable cardiovascular risk factors at screening visit.

# 4. Study Organisation

TRACE RA aims to randomise up to 5350 RA patients, from up to 120 centres in the United Kingdom (UK). The aim is to continue recruitment until the required number of participants has been recruited to accrue sufficient person years of follow-up to achieve study power (see Section 10). The study commenced in August 2007, and recruitment is currently planned to continue until March 2014, with completion of follow up currently planned for March 2016.

The Chief and Lead Investigators plus the Trial Manager form an executive trial core management committee (TCMC). There are trials units based in Dudley, Dundee and Manchester, which oversee the management of this trial according to ICH GCP. The trials units support their affiliated recruiting centres and monitor data management for the trial. Each recruiting centre agrees affiliation to one of the trials units prior to participating in the study. However, it may be necessary to make some changes during the trial to balance the workload between trial units.

Data from all recruiting centres are being collected at the AR UK Epidemiology Unit, University of Manchester, who maintain overall responsibility for all trial data, and for the Standard Operating Procedures (SOPs) that describe how the trial is to be conducted within participating trials centres and units. All data are handled, computerised and stored in accordance with the Data Protection Act 1998. Quality control of data is maintained by the University of Manchester through regular meetings to discuss data management with the other trials units. The trials units (Dudley, Dundee and Manchester) are responsible for checking case report forms (CRFs) for compliance with the protocol, inconsistent and missing data, and for resolving data queries.

Data and statistical analysis is overseen by the Trial Statistician, [name], who is based at the Wellcome Trust Clinical Research Facility in Birmingham.

# 5. ELIGIBILITY CRITERIA

### Inclusion criteria:

- Patients who satisfy 1987 ACR classification criteria for RA applied cumulatively [71]
- Age ≥50 years **OR** RA disease duration ≥10 years
- Written informed consent

### Exclusion criteria:

- Already taking a statin
- Known cardiovascular disease deemed to require statin therapy

i.e. previous episodes of confirmed Acute Coronary Syndrome (ACS), unstable angina; myocardial infarction with or without ST elevation; or stable CHD/CVD deemed to require statin therapy on clinical grounds, including:

- → Previous amputation due to severe peripheral vascular disease or current peripheral arterial disease
- → Previous central or peripheral revascularisation procedure (including angioplasty or stent, artery bypass graft surgery)
- → Accelerated hypertension, severe heart failure (class III or IV), significant dysrhythmia or angina requiring hospitalisation in the 6 months preceding potential study entry
- → Uncontrolled hypertension (treated or untreated) defined as systolic blood pressure > 200 mmHg and/or diastolic blood pressure > 110 mmHg (identified as the disappearance of all sound (Korotkoff Phase V) after sitting quietly for at least 3 min)
- → Previous cerebrovascular accident
- → Other accepted indication for statin therapy according to the investigator's current clinical practice
- Diabetes
- Regular use of contra-indicated drugs see below:

### Contra-indicated drugs:

### Statins:

Atorvastatin (Lipitor), Fluvastatin (Lescol), Lovastatin (Mevacor), Pitavastatin (Livalo), Pravastatin (Lipostat), Rosuvastatin (Crestor), Simvastatin (Zocor),

### Other contra-indicated drugs:

e.g. amiodarone, azole anti-fungals (fluconazole, ketoconazole, itraconazole), ciclosporin, fibrates, HIV protease inhibitors, macrolide antibiotics (erythromycin, telithromycin, clarithromycin), niacin, veramapil

Drugs known to affect lipid levels

#### e.g. colestipol, ezetimibe

### Other exclusions:

- Primary muscle disease or CK >3 x ULN
- Known familial hyperlipidaemia

- Acute liver disease
- Severe renal dysfunction (Stage 3 or 4) or creatinine > 200 micromol/l or receiving renal replacement
- Uncontrolled hypothyroidism
- Hypersensitivity or intolerance to statins
- Pregnant, breast feeding or of child bearing potential not using adequate contraception\*
- Alcohol abuse
- Participating in another Clinical Trial of Investigational Medicinal Product (CTIMP)
- Drinking more than 240ml of grapefruit juice per day
- Any other serious illness that may compromise safety or trial compliance

\*Adequate contraception for the purpose of this trial will include the following:

### **Barrier Method:**

Male condom Female condom Contraceptive Diaphragm Cervical cap Contraceptive Sponge Diaphragm cleaning Vaginal Spermicide Intrauterine Devices

### **Endocrine Method:**

Combined oral contraceptives Minipills Injectable progestins Implantable progestins

### **Surgical Sterilization**

Female sterilization Male sterilization

# 6. TRIAL PROCEDURES

### 6.1 Patient selection and informed consent

Once a patient has been selected based on the eligibility criteria, sufficient time is provided for the patient to decide on trial entry, but the time which elapses between randomisation and start of treatment should be minimised (ideally no longer than four weeks).

Potentially eligible RA patients are identified from their medical records based on the presence of inclusion/exclusion criteria using the Trial Screening Form. Information on the trial is given to potentially eligible patients and they are asked to give their written informed consent. Patients are checked to ensure they are not already on a statin and do not have an existing indication for a statin according to standard clinical practice.

The Registration Form is faxed to the Manchester TRACE RA Office within 24 hours of registering a patient to the trial. A schedule of the patient's visits ('PCA' – Patient Clinical Assessments) is sent to the recruiting centre to confirm receipt of the registration form.

All other documents (copy of consent forms, baseline data ('baseline/randomisation' form'), questionnaires, eligibility checklists) should be posted to the Manchester TRACE RA office within 7 working days.

# Trial ID numbers are provided on pre-printed Patient details logs – a trial number from the CRF used for each patient is the patient's trial number for the duration of the trial.

### 6.2 Trial investigations:

### (Please see Appendix 10 for Trial Evaluation Schema)

Local routine practice is followed with regards to screening for 10 year cardiovascular risk. Recruiting centres that routinely screen for CVD risk continue to do so and those that do not continue to not screen. Therefore there is no requirement to measure the lipid profile of patients prior to trial entry in centres that do not routinely measure patients' CVD risk. Where a centre routinely measures CVD risk, we recommend that the JBS2 risk calculator is used

(http://www.bhsoc.org/Cardiovascular\_Risk\_Charts\_and\_Calculators.stm)

### 6.2.1 Baseline/randomisation visit

Patients are given the opportunity to ask any questions they may have, and then asked to provide their written informed consent to enter the study.

- Following this the patient has the following recorded:
  - → Medical history
  - $\rightarrow$  Smoking status
  - $\rightarrow$  Record of concomitant medication
  - $\rightarrow$  DAS 28 tender and swollen joint counts
  - $\rightarrow$  Height, weight and blood pressure
- Participants are asked to complete the following questionnaires:
  - $\rightarrow$  Patient global assessment (VAS)
  - $\rightarrow$  HAQ [72] and EQ5D [73] questionnaires
  - → Lifestyle factor questionnaire
- And asked to give a blood sample:
  - → ESR and/or CRP tests: if results are available from within the last 6 weeks while their treatment has remained unchanged and the patient is stable then these results may be used instead;
  - → RhF (rheumatoid factor) and/or anti-CCP (anti-cyclic citrullinated peptide antibody): if results are available from previous points during the course of their RA, then these results may be used instead.

All patients are also asked to consent to the optional TRACE RA BioBank sub study (Appendix 2).

### • For TRACE RA-BioBank sub study participants (Optional)

- $\rightarrow$  2 x 10mls plasma blood sample
- $\rightarrow$  2 x 10mls serum (clotted) blood sample
- $\rightarrow$  2 x 10mls EDTA blood sample (for DNA) (immediately stored at -80°C)
- $\rightarrow$  1 x 4.5mls plasma (citrate) blood sample

Patients who have a DAS28 score of  $\geq$ 3.2 may be asked to consent, in addition, to the TRACE RA DAS sub study (Appendix 1). The DAS28 (Disease Activity Score) [74] will be calculated using the most recent ESR/CRP. Outcome measures will be recorded in the CRF and patient hospital notes (See Appendix 6). **This sub study will only be run at selected centres**.

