With the exception of ciclosporin (which is metabolised through cytochrome P450 and can thus increase the risk of myopathy when used with some statins) there are no known significant interactions between anti-rheumatic drugs and statins. Statins are useful for secondary and primary prevention, in patients with overt CHD or those with a 10-year CVD (CHD+stroke) risk of >20%. Recent work shows that this is the case also for low risk patients, e.g. patients with diabetes with a <15% CHD risk [61]. Whereas many statin-effects may be class effects, there is evidence to suggest individual differences. Atorvastatin appears suitable for this pragmatic study. Several studies have shown a good safety profile over a wide dose range with no need to adjust dose for renal impairment. Improvements in cardiovascular end-points have been shown in many different settings and clinical populations such as ACS, stable CHD, diabetes and hypertension, including low CV risk diabetics. Early benefits seen in some atorvastatin studies have not been seen with other statins, particularly simvastatin, whereas newer statins (e.g. rosuvastatin) currently lack a large body of endpoint data. Atorvastatin may also have better effects on plaque progression and inflammatory marker reduction than either pravastatin or simvastatin [62-68]. Atorvastatin is also the only statin that has been used in an RA population with some "proof of concept"

that, at a dose of 40mg daily, it can reduce systemic inflammation and improve lipid profile in RA [60], and has been shown to reduce arterial stiffness in patients with RA [69].

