### TRACE RA-DAS (sub-study only):

EULAR moderate or good response based on DAS 28 at 6 months

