#### A1.2 Study Design

A multicentre, randomised, double blind, placebo-controlled trial of atorvastatin 40mg once daily for control of disease activity in patients with RA aged  $\geq$ 50 years or with  $\geq$ 10 years of RA disease duration (if under 50 years of age). This is a sub-study of the main TRACE RA trial which explores the influence of atorvastatin on cardiovascular endpoints.

A total of **326** *patients* will be required and each patient will be followed for two years (with respect to the sub-study but will also be followed up until the end of the cardiovascular/main study).

The inclusion and exclusion criteria for the disease activity sub-study are similar to the main study with the express *proviso that all patients entering the sub-study must have a baseline DAS28 score of*  $\geq$  3.2.

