#### A1.3 Proposed Duration of Treatment, Follow up and Frequency of Intervention

Patients participating in this substudy will have an additional nurse global assessment and be asked to provide a blood sample for mRNA, serum and plasma extraction at baseline and month 6 of their trial visit. (As outlined in Appendix 2)

Patients will also have the following assessment in Months 6, 12, and 24: 28 tender and swollen joint counts Patient global assessment Nurse global assessment ESR and/or CRP

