#### A1.4 Proposed Sample Size

A sample size of 326 patients is required to provide 80% power at the 5% significance rate to detect a difference in EULAR response rate between statin treated and the placebo arms. This assumes a 20% response rate in the placebo arm and 20% loss to follow-up during the 2 years of the sub-study.

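### TRACE RA DAS: nothing ties the follow-up blood marker to the baseline marker, so the DAS28 change behind EULAR response can mix an ESR-based and a CRP-based score

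*Protocol*

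**What the plan says.** Section 3.1 defines the sub-study primary endpoint as "EULAR moderate or good response based on DAS 28 at 6 months". Section 3.2 adds DAS28 at months 12 and 24 as secondary.

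For the baseline blood test, section 6.2.1 reads "ESR and/or CRP tests: if results are available from within the last 6 weeks while their treatment has remained unchanged" and also requires the patient to be stable; such a result may replace a new sample. The same section then states, for sub-study entry, "The DAS28 (Disease Activity Score) [74] will be calculated using the most recent ESR/CRP".

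For follow-up, Appendix 1 (A1.3) lists the month 6, 12 and 24 assessments as "28 tender and swollen joint counts Patient global assessment Nurse global assessment ESR and/or CRP". Section 6.2.3 lists the same open choice of marker at those three visits.

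Entry depends on the same score: A1.2 says "all patients entering the sub-study must have a baseline DAS28 score of" 3.2 or more. No section names a DAS28 version or links the follow-up marker to the one used at baseline.

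**The concern.** EULAR response classifies each patient by the drop in DAS28 and the level reached. That works only if both scores come from the same instrument. ESR-based and CRP-based DAS28 use different weights and a different constant, so they can differ in a patient whose disease has not changed. A centre that uses ESR at baseline and draws only CRP at month 6 follows the text exactly, and the patient's recorded change then includes a change of instrument. This can create a response or hide one, and the 3.2 entry threshold does not mean quite the same thing at every centre.

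This is a rule about what is collected. An analysis plan can name the formula, but it cannot by itself supply a marker that was not measured, so the point belongs in the protocol.

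**Working it through.** **1. The sub-study's own figure, as the reference point.** A1.4 says "A sample size of 326 patients is required to provide 80% power at the 5% significance rate", with 20% placebo response and 20% loss. The treated-arm rate is not stated. With an assumed 35%, unpooled variance and a two-sided 5% level:

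n per arm = (1.96 + 0.842)² × (0.20×0.80 + 0.35×0.65) / 0.15² = 135.2, so 136; total 272; 272 × 1.2 = 326.4.

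This matches 326, so 20% versus 35% is used below, as an inference. After 20% loss, 326 × 0.8 = 260.8, about 130 evaluable per arm. Power at 20% versus 35% (normal approximation, pooled null variance, equal allocation assumed) is then 77.6%.

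**2. What a marker switch does to one patient.** Assumed formulas, not given in the protocol:

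- DAS28-ESR = 0.56√TJC + 0.28√SJC + 0.70 ln(ESR) + 0.014 GH
- DAS28-CRP = 0.56√TJC + 0.28√SJC + 0.36 ln(CRP+1) + 0.014 GH + 0.96

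TJC and SJC are the tender and swollen joint counts, and GH is the patient global score in mm. Take 6 tender joints, 4 swollen, global 50 mm, ESR 28 and CRP 10:

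- ESR version: 1.37 + 0.56 + 2.33 + 0.70 = 4.96
- CRP version: 1.37 + 0.56 + 0.86 + 0.70 + 0.96 = 4.45

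The joint and global terms cancel, so the gap is 0.70 ln(ESR) − 0.36 ln(CRP+1) − 0.96. With CRP 10:

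| ESR | Gap |
|---|---|
| 28 | 0.51 |
| 20 | 0.27 |
| 15 | 0.07 |

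The gap varies from patient to patient and may be negligible.

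**3. What it does to response.** A simulation assumed baseline DAS28 with mean 4.6 and SD 1.0, truncated at 3.2, and change with SD 1.0. Response was a drop above 1.2, or above 0.6 with a final score of 5.1 or less. These EULAR cut-offs are also assumed. The mean change was set to give 20% (placebo) or 35% (treated). A constant shift was then added:

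| Shift | Placebo rate | Treated rate | Effect in the placebo arm |
|---|---|---|---|
| +0.2 | 26.0% | 42.6% | response created in 7.5% of true non-responders |
| +0.4 | 32.7% | 50.5% | created in 15.9% |
| −0.2 | 14.9% | 28.0% | 25.4% of true responses hidden |
| −0.4 | 10.8% | 21.8% | 46.2% hidden |

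These rates apply only to patients who switch marker.

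**4. What it does to the comparison.** Let a share s of patients switch, half in each direction and alike in both arms: rate = (1−s)·f(0) + (s/2)·f(+δ) + (s/2)·f(−δ), where f is the response rate under a shift. For s = 30% and δ = 0.4:

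- Placebo: 0.7×0.200 + 0.15×0.327 + 0.15×0.108 = 0.205
- Treated: 0.7×0.350 + 0.15×0.505 + 0.15×0.218 = 0.353

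Power with 130 per arm, against 77.6% without switching:

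| Share switching | δ = 0.2 | δ = 0.4 | δ = 0.6 |
|---|---|---|---|
| 10% | 77.5% | 77.1% | 76.5% |
| 20% | 77.4% | 76.7% | 75.3% |
| 30% | 77.3% | 76.2% | 74.2% |

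The loss is 0.1 to 3.4 points. If by chance 10 percentage points more patients switched in one arm, all upwards by 0.2 to 0.6, the placebo-rate calculation moves that arm's rate by 0.6 to 2.0 points.

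**The case against.** The strongest reply is that the effect on the sub-study is small and its size comes from outside the document. That stands. The protocol gives no formula, no offset between markers and no switching frequency, and the 0.51 example shrinks quickly with a lower ESR. Treatment is randomised and double blind, so switching should be similar in both arms. The main cardiovascular endpoint is untouched.

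Three stronger readings are tempting, and the document does not support them:

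- *Bias in favour of atorvastatin.* Section 2.1.4 says "Atorvastatin may also have better effects on plaque progression and inflammatory marker reduction", but it compares atorvastatin with other statins. A drug that lowers the blood component would affect any DAS28, and holding one marker fixed would not change that.
- *A baseline blood result of any age.* The sentence on the most recent result sits in section 6.2.1, which limits reuse to 6 weeks, unchanged treatment and a stable patient. Those safeguards are reasonable.
- *Mixed scores can never be repaired.* Sections 6.2.1 and 6.2.3 and Appendix 2 (A2.3b) provide for serum and plasma from sub-study patients at baseline and month 6, so a matching CRP may be recoverable. Recovery is only partial: A2.3a notes that some centres may not be able to supply serum and plasma, A1.8 sends requests to use samples to an ethics committee, and no stored samples are listed for months 12 and 24.

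A standard operating procedure, case report form or analysis plan not at hand might name the DAS28 version, and its absence here is not criticised. The same-marker collection rule is different, because a centre working from the protocol needs it before blood is drawn.

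**Conclusion.** The point holds in limited form. The protocol lets the within-patient DAS28 change combine two instruments. That adds avoidable, largely non-differential misclassification to the sub-study primary endpoint, to the DAS28 secondary endpoints at months 12 and 24, and to the entry threshold. Individual classifications can change materially, while the average cost is about 0 to 3 points of power if 10-30% of patients switch in balanced directions by 0.2-0.6 units. The size rests on the assumed formulas, EULAR cut-offs, DAS28 distribution, treated-arm rate and switching share. The gap in the wording does not depend on those assumptions. It is worth correcting because the correction costs little, not because the sub-study result would otherwise be invalid.

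**What to change.** In sections 6.2.1 and 6.2.3 and in A1.3, for sub-study patients:

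- Require the same marker, with the matching DAS28 version, at baseline and at months 6, 12 and 24. A centre may choose the marker but keeps it for that patient.
- Record on the case report form which marker and version were used.
- Calculate EULAR response only from same-marker scores.

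For patients already enrolled, use the marker available at both visits. Where there is none, and where feasible and approved, assay CRP from banked baseline and month-6 serum or plasma. Any patient still without a matching pair has a missing response and is handled under section 10.5.

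The baseline allowance for a result up to 6 weeks old may stay; a same-day draw is optional. The sample size of 326 does not change. The cost is wording, one recorded item, and some centres having to make sure that the baseline marker is repeated at follow-up. Blood is already taken at baseline and month 6, and a marker is already listed at months 12 and 24.

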### • For TRACE RA DAS sub study participants (Optional)

- $\rightarrow$  Nurse global assessment (VAS)
- $\rightarrow$  Bloods taken as for the Biobank study (as outlined above) PLUS
- $\rightarrow$  4 x 2.5mls blood sample (for RNA testing) on two occasions (baseline and 6 months)

All patients are counselled by the study nurse or doctor about modifiable cardiovascular risk factors, e.g. smoking or obesity (BMI>30kg/m^2) and given a copy of a leaflet prepared for the TRACE RA trial. GPs are informed of all significant clinical issues found at the screening visit using a standard letter.

Patients are then randomised to either the atorvastatin arm (40mg of atorvastatin oral tablet taken once daily) or placebo arm (placebo atorvastatin oral tablet taken once daily) of the trial. The patient is also registered with the trials units in order to obtain confirmation of the trial number for analysis of their medical information and subsequent dispatch of the trial drug.

### 6.2.2 Allocation of patients to trial treatment arm

Allocation of patients to trial treatment arm: The study is double blind with matching placebo. Neither patients, investigators nor trial units are aware of the treatment allocation. The medication is provided by Pfizer UK Ltd., bottled by an independent pharmaceutical company (Catalent Pharma Solutions UK Limited) to GMP standards and dispensed by the local study pharmacist. The randomisation process is incorporated into the drug labelling. Each patient is allocated a filled and labelled bottle coded with a unique drug number when entering the trial. All future supplies for this patient will be coded with the same unique drug number. Patients will continue on the same treatment (i.e. active or placebo) throughout the duration of the study. Scratch cards are supplied to the local pharmacy so that the code can be broken if necessary. Catalent Pharma Solutions provides the independent trial statistician with information about treatment allocation by unique drug number to enable the interim analyses to be conducted. A TRACE RA Standard Operating Procedure is in the study site file for further information on providing treatment to patients.

### 6.2.3 Follow-up visits for TRACE RA participants

Patients are asked to attend visits at **3 months**, and then **6-monthly from randomisation**. When attendance is not possible the CRF may be completed by telephone interview, however, every effort will be made to have an actual attendance to clinic at least once a year - in many cases this may coincide with the patient's routine clinic visit appointment. If patients are to continue study treatment, preferably ALT (and if ALT not available then AST) measurements are mandatory within **6 weeks** of the follow-up visit - the overwhelming majority should be available through the patient's routine DMARD monitoring.

